## **BACKGROUND/SCIENTIFIC RATIONALE**

---

Alcohol use is the third leading global contributor to the burden of disease (World Health Organization, 2009) and costs of excessive alcohol use in the United States exceeded \$220 billion in 2006 dollars (Bouchery, Harwood, Sacks, Simon, & Brewer, 2011). One-third of Americans meet lifetime criteria for alcohol use disorder (AUD) and 8.5% meet criteria for current AUD (Hasin, Stinson, Ogburn, & Grant, 2007). Of those with AUD who receive behavioral or pharmacological AUD treatment, most return to drinking within the first year following treatment ([name] & Marlatt, 2004; [name] & Masyn, 2008; [name], 2008). As such, AUD has been characterized as a chronic relapsing disease (Leshner, 1997; McLellan, Lewis, O'Brien, & Kleber, 2000). Behavioral interventions for AUD are the most common form of treatment; however, increased understanding of the neurobiological dysfunction associated with addiction (Goldstein & Volkow, 2002; Koob & Volkow, 2010; Koob, 2006) has led to greater interest in treatment approaches that target specific neural systems (Goldstein & Volkow, 2002; Koob, 2006; Koob et al., 2014; Litten et al., 2015). The proposed study will evaluate the efficacy of combining two approaches designed to target behavioral and neurobiological dysfunction in addiction: mindfulness-based relapse prevention (MBRP) (Bowen et al., 2014; [name], Bowen, Douglas, & Hsu, 2013; [name] & Bowen, 2010; [name], Lustyk, & Bowen, 2013; [name], Marlatt, & Walker, 2005; [name], Warner, et al., 2014) and transcranial direct current stimulation (tDCS) (Feil & Zangen, 2010; [name] & [name], 2015). The ultimate goal of this research is to develop a more efficacious intervention for reducing heavy drinking that has minimal side effects and great potential for large-scale dissemination.

Mindfulness-based relapse prevention (MBRP) for substance use disorders may be an ideal behavioral intervention for helping individuals cope with acute, cue-induced craving because it was designed to target experiences of craving and their role in the relapse process (Bowen et al., 2010; Brewer et al., 2011; [name] et al., 2005). Based on the results of numerous studies, MBRP is a feasible and efficacious behavioral treatment for substance use disorders (Bowen et al., 2009; Bowen et al., 2014; [name] et al., 2014). The recent use of tDCS over task relevant regions to alter behavior and improve learning holds incredible promise for use in cognitive behavioral intervention protocols. This proposed study will attempt to enhance learning of mindfulness practices that are taught in MBRP by providing tDCS during brief mindfulness training (BMT). The objective of this study is to establish the feasibility and obtain preliminary data on the effectiveness of using tDCS with MBRP to reduce heavy drinking.

Chronic alcohol use is strongly associated with poor behavioral and cognitive control (Bechara & Damasio, 2002; Bechara, Dolan, & Hindes, 2002; Goudriaan, Grekin, & Sher, 2007). Imaging studies, have found that AUD is associated with altered functioning in brain regions that support cognitive control such as dorsolateral prefrontal cortex (dlPFC), inferior frontal gyrus (IFG), and anterior cingulate cortex (ACC) (Claus, Feldstein Ewing, Filbey, & Hutchison, 2013; Pfefferbaum et al., 2001; Sullivan & Pfefferbaum, 2005) and degree of AUD severity predicts differential brain responses in these regions when performing cognitive control tasks. For example, in a functional magnetic resonance imaging (fMRI) study, Claus and colleagues (Claus et al., 2013) found severity of AUD was negatively associated with blood oxygen level dependent (BOLD) signal change in right IFG, pregenual ACC, and

inferior parietal lobe (IPL) during correct inhibition trials; and bilateral IFG and dorsal ACC during error trials of a Go/NoGo cognitive inhibition task. Using electroencephalography (EEG), numerous studies have found deficits in attention allocation, as evidenced by a decrement in P3 (e.g., P300) amplitudes during cognitive inhibition tasks among individuals with AUD and among individuals at risk for AUD, based on family history of AUD (Porjesz et al., 2005). Consistent with these findings, a combination fMRI-EEG study found that lower P3 amplitudes among subjects who were high-risk for AUD had significantly less activation in the bilateral IPL and reduced activation in the bilateral IFG as compared to subjects who were low-risk for AUD (Rangaswamy et al., 2004).

Numerous studies have provided support for the importance of craving (defined as the subjective desire to drink) in the relapse process and for the association between reactivity to alcohol cues, self-reported craving, and drinking outcomes (Claus, Ewing, Filbey, Sabbineni, & Hutchison, 2011; E. L. Garland, Franken, & Howard, 2012; Litt, Cooney, & Morse, 2000; [name] & Marlatt, 2004; [name], 2013). Imaging work has consistently shown a diverse network of regions involved in cue reactivity such as ACC, ventral and dorsal striatum, orbitofrontal cortex (OFC), insula, and brainstem (Claus, Ewing, Filbey, Sabbineni, & Hutchison, 2011; Myrick et al., 2008; Schacht, Anton, & Myrick, 2013; Vollstädt-Klein et al., 2010). In a large sample (n=326) of individuals with AUD who completed a cue reactivity task and found that increased AUD severity was associated with greater engagement of ventral and dorsal striatum, ACC, amygdala, and precuneus during cue presentation (Claus, Ewing, et al., 2011). EEG studies have found increased P3 amplitudes in response to alcohol cues among individuals at risk for AUD (Bartholow, Lust, & Tragesser, 2010) and among AUD patients (Heinze, Wölfling, & Grüsser, 2007; Namkoong, Lee, Lee, & An, 2004), suggesting greater salience and motivational significance of alcohol cues (Bartholow, Henry, & Lust, 2007).

Reactivity to stress and negative affect is commonly considered one of the hallmark features of addiction (Koob, 2006; Sinha & Li, 2007). Our own work has found self-reported negative affect to be a primary predictor of alcohol relapse ([name] & Marlatt, 2004; [name] & Villarroya, 2009; [name], 2011). Engagement of stress circuitry that includes the hypothalamic-pituitary-adrenal (HPA) axis and extended amygdala plays a key role in the development of stress and negative affect reactivity in AUD (Koob & Le Moal, 2008; Koob, 2006; Koob et al., 2014; Sinha et al., 2003). Resting EEG, including decreased alpha power (8-13 Hz) and increased theta (4-8 Hz) and beta power (13-30 Hz) has been associated with both stress response and addiction (Enoch et al., 2008; Hodgkinson et al., 2010).

Mindfulness can be defined as the awareness that arises through paying attention to the present moment in a purposeful and non-judgmental way. Mindfulness based interventions (MBIs) have been shown to be efficacious in reducing alcohol use (Chiesa & Serretti, 2013; [name], Bowen, et al., 2014; Zgierska et al., 2009). Extant research suggests that MBIs might be effective in part by reducing craving (Bowen et al., 2009), decoupling the negative affect-craving association ([name] & Bowen, 2010), decoupling the craving-substance use association (Elwafi, [name], Mallik, Iv, & Brewer, 2012), increasing the mindfulness-based processes of awareness, acceptance, and nonjudgment ([name], Bowen, et al., 2013), and decreasing maladaptive responses to craving (Bowen, [name], Dillworth, & Marlatt, 2007; Garland & Gaylord, 2010; Gifford et al., 2004).

Previous reviews of neuroimaging studies have posited several putative neural mechanisms of mindfulness (Brewer, Elwafi, & Davis, 2013; Chiesa, Brambilla, & Serretti, 2011; Chiesa, Brambilla, & Serretti, 2010; Chiesa, Serretti, & Christian, 2013; Hölzel et al., 2011; [name], Lustyk, & Bowen, 2013). In healthy adults, 8 weeks of MBI was found to be associated with decreased functional connectivity between right insula and ventromedial prefrontal cortex (vmPFC) when mindfully attending to internal states (Farb et al., 2007), and increased right insula activation following sadness provocation (Farb et al., 2010). In a sample of smokers, decreased functional connectivity between the insula and the subgenual ACC was found when mindfully attending to smoking images compared to passively viewing the images, suggesting a decreased association between these reward regions (Westbrook et al., 2011). An EEG study examining P3 amplitudes during a Go/NoGo task found increased P3 amplitudes during inhibition among individuals with attention deficit hyperactivity disorder who received eight weeks of MBI, as compared to control; suggesting MBIs may increase inhibitory control (Schoenberg et al., 2014). In summary, MBIs may improve functional connectivity between the ACC

and dlPFC, as well as reduce the connectivity between the insula and vmPFC ([name], Lustyk, & Bowen, 2013), which may contribute to increases in awareness and decreases in craving observed among AUD patients who receive MBIs ([name], Bowen, et al., 2013).

PI [name] has conducted three randomized clinical trials (RCTs) evaluating mindfulness-based relapse prevention (MBRP) as a treatment for substance use disorder (Bowen et al., 2009, 2014; [name], Warner, et al., 2014). MBRP is a manualized intervention combining cognitive behavioral skills with brief mindfulness training (BMT). Two RCTs have examined MBRP delivered as aftercare following inpatient or outpatient treatment as compared to (1) treatment as usual (TAU, which consisted of psychoeducation, relapse prevention, and 12-step groups) (Bowen et al., 2009); or (2) TAU and relapse prevention (RP) (Bowen et al., 2014). In both studies MBRP was associated with significantly fewer alcohol and drug use days (Cohen's  $d=0.28$ ) at 2-month (Bowen et al., 2009) and 12-month (Bowen et al., 2014) follow-ups. A third RCT examined MBRP as the primary intervention and found MBRP was significantly more effective in reducing alcohol and drug use days compared to RP (Cohen's  $d=0.36$ ) at a 15 week follow-up ([name], Warner, et al., 2014).

Thus, data from three RCTs provide support for the efficacy of MBRP, as compared to alternative empirically supported treatments. Yet, the effect sizes are still small in magnitude and each of the former trials has been limited by considerable dropout and low engagement. MBRP treatment compliance rates range from 50-60% of participants attending the majority of sessions (Bowen et al., 2009, 2014; [name], Warner, et al., 2014), as compared to compliance of 70% in RP (Bowen et al., 2014; [name], Warner, et al., 2014). Clinically, we have observed participants struggle with the mindfulness practices, perhaps due to significant deficits in executive function (Aharonovich et al., 2006) and inhibitory control (Brewer, Worhunsky, Carroll, Rounsaville, & Potenza, 2008; Streeter et al., 2008). Those clients who are able to engage with MBRP experience fewer and less severe lapses, as well as report greater improvements in overall quality of life ([name], Warner, et al., 2014).

Transcranial direct current stimulation (tDCS) is a safe and non-invasive brain stimulation technique that applies weak electrical current to stimulate brain regions ([name] et al., 2011; Coffman et al., 2012; Falcone, Coffman, [name], & Parasuraman, 2012; Jacobson, Koslowsky, & Lavidor, 2012). Most tDCS studies compare active (1.0 to 2.0 milliamps (mA)) tDCS to a sham/control condition with either reduced current strength (i.e., 0.1 mA) or a ramp-up/ramp-down procedure that introduces a modest current for a brief amount of time. Active tDCS versus sham has been shown to enhance the effects of cognitive training in a number of domains, including memory, attention and other forms of cognition. One study found that tDCS produced a doubling of performance accuracy in a learning task (Falcone et al., 2012). There have been over 250 clinical trials using tDCS for a variety of disorders and diseases, with promising effects of tDCS in treating symptoms of schizophrenia (Brunoni et al., 2014), major depression (Shiozawa et al., 2014), Alzheimer's disease (Hansen, 2012), chronic pain (O'Connell, Wand, Marston, Spencer, & Desouza, 2014), and stroke (Bastani & Jaberzadeh, 2012). There are also preliminary data suggesting tDCS has an effect on addictive disorders (Feil & Zangen, 2010).

The neurobiological mechanisms of tDCS depend on a variety of factors, including current strength and duration; the number, polarity and specific placement of electrodes; the electrode composition and size; and individual differences in physiology. TDCS has been shown to alter neuronal activity, cerebral blood flow, synaptic transmission, oscillatory activity, functional connectivity, and neurotransmitter concentrations ([name], Coffman, Trumbo, & Gasparovic, 2011; Hansen, 2012; Kim, Stephenson, Morris, & Jackson, 2014). **The placement we plan to use in the proposed research, which we have used successfully in our prior work, is up to 2.0 mA of anodal stimulation of the right IFG (i.e., BA F10) with a left upper arm cathode.**

[figure not shown]

Figure 1. Modeled current distribution for IFG (anode) and contralateral arm (cathode) placement using FEM [Courtesy of [name] and [name], CCNY]

Modeling of the electrical fields induced by the right IFG vs. left arm montage using finite element modeling (FEM (Datta, Bikson, & Fregni, 2010; Datta, Truong, Minhas, Parra, & Bikson, 2012), Figure 1), suggests that the largest effect is located underneath the anodal electrode, in the right IFG, including pars orbitalis, posteriorly into pars triangularis and to a lesser extent into the medial frontal regions. Increased excitability is also observed in the inferior aspect of the right temporal pole extending along the inferior temporal gyrus, the right OFC, and the right anterior insula. Subcortically, the strongest fields are located within white matter tracts surrounding the right striatum, portions of the right medial temporal lobe, and the inferior aspect of the cerebellum, including adjacent white matter regions connecting these structures. In addition to these regions, activity in other regions to which these areas are interconnected may also be altered. These may include a large portion of cortex, as well as higher-order areas that mediate cognitive and affective processes that may facilitate the ongoing acquisition and maintenance of mindfulness and produce benefits for treating AUD. Importantly, tDCS has been shown to impact the behavioral targets of the proposed study in healthy controls and patient samples, with active tDCS effects on inhibitory control (Levasseur-Moreau & Fecteau, 2012; Stramaccia et al., 2015), cue-reactivity and craving (Jansen et al., 2013; Nardone et al., 2012), and negative affective reactivity (Plewnia, Schroeder, Kunze, Faehling, & Wolkenstein, 2015; Pripfl & Lamm, 2015).

Most investigations of tDCS for addictive disorders have focused on intermediate phenotypes, including effects of tDCS on decision making and cue reactivity among individuals with stimulant use disorders (Conti, Moscon, Fregni, Nitsche, & Nakamura-Palacios, 2014; Conti & Nakamura-Palacios, 2013; Shahbabaie et al., 2014), smoking and nicotine use disorders (Boggio et al., 2009; Fecteau et al., 2014; Fregni et al., 2008), and marijuana use (Boggio et al., 2010). The growing literature of tDCS studies conducted with heavy drinkers and AUD patients have found significant effects of active tDCS on reductions in alcohol craving (Boggio et al., 2008; Den Uyl, Gladwin, & Wiers, 2015; Jansen et al., 2013; Nardone et al., 2012) and one small pilot RCT found significant effects of tDCS in preventing relapse and improving quality of life among patients with AUD (Klauss et al., 2014).

AUD has been characterized as a chronic relapsing condition (McLellan et al., 2000) with hallmark features that include loss of inhibitory control, heightened salience of alcohol cues and experiences of craving, and persistent negative affect. Each of these hallmark features has been successfully targeted independently with two novel interventions: mindfulness-based intervention and tDCS. Mindfulness-based interventions have enduring effects, but treatment engagement remains a barrier to success. Given effects of tDCS on improvements in state mindfulness and executive functioning in our prior studies (described below), **we hypothesize that tDCS could significantly increase engagement with mindfulness training.** Both tDCS and mindfulness have independently shown benefits for treating AUD. The combination of tDCS and mindfulness may provide synergistic benefits to reducing symptoms of AUD greater than each can provide alone. The proposed study will provide a sufficiently powered, sham-controlled double blind investigation of the efficacy of MBRP in combination with active tDCS as an intervention for AUD. The design will also allow us to examine changes in inhibitory

control, cue reactivity and craving, negative affect reactivity, and cognitive behavioral skills training acquisition as mechanisms of behavior change following the intervention.

Many individuals with AUD never receive treatment (Substance Abuse and Mental Health Services Administration, 2014). For those who seek care, relatively few efficacious treatments are available (Jonas et al., 2014; National Institute for Health and Care Excellence, 2011; Zindel & Kranzler, 2014). The low rates of utilization of treatments for AUDs and the modest efficacy of existing interventions underscore the need to develop and test new treatments that are more efficacious and attractive to patients. **Mindfulness-based interventions and tDCS are already being developed and marketed for at-home use** (Conti et al., 2014; Fecteau et al., 2014), **while both interventions (MBRP and tDCS) are relatively low cost with minimal side effects and have great potential for dissemination.** The application of tDCS can be directed to specific regions of interest allowing for induction of long-term neural plasticity that is regionally specific, a significant advantage over pharmacological treatments that bind to receptors without regional specificity. It may ultimately be possible to personalize tDCS application to specific neural dysfunction, which has important implications for personalized medicine approaches to addiction treatment (Litten et al., 2015).

## OBJECTIVES/AIMS

---

The goal of this study is to examine the efficacy of a MBRP and tDCS intervention in reducing drinking and impacting mechanisms of behavior change among individuals who are interested in reducing their alcohol drinking. The aims of the proposed research are:

**Primary Aim: To examine the efficacy of a mindfulness-based intervention, in combination with active tDCS (up to 2.0 milliamp (mA)) versus sham (0.0 mA) tDCS of the right inferior frontal gyrus (rIFG), in reducing drinks per drinking day.**

Individuals who are interested in reducing their drinking will be recruited from the community and clinician referrals. All participants will receive group MBRP for 8 sessions with each session lasting 2 hours, for up to 8 weeks, and will also be randomized to receive active up to 2.0 mA tDCS or sham 0.0 mA tDCS. Participants will complete weekly self-report measures during treatment and self-report, behavioral, and EEG assessments at baseline, end of treatment, and two months following treatment.

Hypothesis 1. Active tDCS, as compared to sham tDCS, will be associated with significant reductions in drinks per drinking day after treatment and 2 months following treatment.

**Secondary Aim: To examine mechanisms of drinking behavior changes following treatment.**

Hypothesis 2. Effect of active tDCS on drinks per drinking day at the 2-month follow-up will be mediated by greater mindfulness, greater inhibitory control and reductions in cue-reactivity, craving, and negative affect during treatment and at the post-treatment assessment. The effect of the “dose” of treatment, including session attendance and amount of mindfulness practice, on drinks per drinking day at 2-months will be mediated by greater mindfulness and inhibitory control and reductions in cue-reactivity, craving, and negative affect.

Hypothesis 3. Based on prior EEG studies of alcohol use disorder and mindfulness, we hypothesize significantly increased amplitude of the P3 (e.g., P300) component of the event-related brain potential (ERP) during cognitive inhibition and reduced P3 amplitude in response to alcohol cues in the active tDCS group at post-treatment, as compared to sham tDCS. Changes in ERPs among those who receive active tDCS with MBRP will be significantly associated with reductions in drinks per drinking day following treatment.

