**MBRP + tDCS Sessions (2 hour treatment groups + 30 minutes for initial assessments, breathalyzer, pregnancy tests, and withdrawal assessments).** Following the baseline session, participants will begin a series of weekly or twice weekly group MBRP + tDCS intervention sessions for up to eight weeks at the PCNC. To maximize the availability of groups and to accommodate various therapist schedules we will run groups either twice per week for four weeks or once per week for eight weeks. All participants will receive up to 8 two hour sessions of MBRP + tDCS, regardless of the group schedule.

At the beginning of each session the subject will be asked to complete a baseline mood assessment, all participants will be breathalyzed, and fertile female participants will be asked to complete a pregnancy test. Women who are pregnant will not be allowed to complete the study and will be told in private of their pregnancy status. Participants who have a BAC > 0.0 will be rescheduled, given snacks and water until their BAC is reduced to < 0.04 in accordance with NIAAA guidelines, and will be provided a taxi voucher. We will also assess all participants for potential alcohol withdrawal at the time of each tDCS session. If participants show significant signs of withdrawal and/or have a score of 8 or greater on the Clinical Institute Withdrawal of Alcohol Assessment Scale (CIWA), then the research assistant will recommend the subject go to the UNM Hospital for further assessment. Our previous studies with more severely dependent individuals occasionally encountered patients with severe withdrawal, and this protocol was used successfully without any adverse consequences. Subjects with CIWA scores of 8 or greater at any session will be excluded from the research study. These aspects of the study will take approximately 30 minutes to complete.

Subjects will then receive 30 minutes of either active or sham tDCS stimulation, depending on their group assignment. A sensation questionnaire will be administered after 5 minutes of tDCS, 15 minutes, and 25 minutes of tDCS. At the end of tDCS stimulation participants will be asked a few questions regarding their mood and mental state to make sure that they have no lingering effects of the stimulation. After tDCS stimulation the remaining time will be used for MBRP session content (described below).

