## II. *Data Analysis/Statistical Considerations*

**Power analysis and sample size considerations.** We conducted power analyses using effect sizes from a pilot study ( $d=0.64$  and  $d=0.43$  on drinks per drinking day at post- and 2-month follow-up). With desired power  $>0.80$ , a two-tailed  $\alpha < 0.05$ , and three time-points, we will need 70 participants to detect a medium effect of active tDCS + MBRP vs. sham tDCS + MBRP on drinks per drinking day at follow-up. For mediation analyses we will need 74 participants to detect a medium effect. Attrition of 15% is anticipated based on our pilot tDCS study and thus we propose to recruit  $n=86$  participants to allow for some attrition. We anticipate screening up to 350 participants in order to recruit a sample of 86 participants.

**Data Analyses and Missing Data.** The primary study aim is to test the overall efficacy of the active tDCS + MBRP intervention compared to a sham tDCS + MBRP group. We will use maximum likelihood estimation for all analyses, which provides the variance-covariance matrix for all available data and is the preferred method for estimation when some data are missing. Variables associated with missing data and those used in randomization (gender, age, treatment history) will be covaried in all analyses.

**Aim #1: Efficacy Analyses.** All assessment data will be analyzed for outliers and missing cases to detect any bias that might result from differential attrition. The efficacy of active tDCS + MBRP versus sham tDCS + MBRP will be examined using a generalized linear mixed model with drinks per drinking day at the end of treatment and follow-up as the primary outcomes. We hypothesize active tDCS will be associated with significantly larger reductions in drinks per drinking day following treatment, as compared to sham tDCS. Interim analyses to compare sham versus active tDCS treatment efficacy will be conducted in February 2017, after a sufficient number of subjects have been treated, and at the time of submitting our annual progress report to NIH, which will occur in June 2017.

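### The dose part of Hypothesis 2 treats non-randomised attendance and practice as causes of less drinking, although the session rules make attendance depend partly on drinking

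*Combined protocol and SAP*

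**What the plan says.** The Secondary Aim (Objectives/Aims, Hypothesis 2) has two parts. The first concerns mediation of the randomised tDCS effect. The second concerns the effect of treatment dose, described as "session attendance and amount of mindfulness practice, on drinks per drinking day at 2-months will be mediated by greater mindfulness and inhibitory control", together with lower cue-reactivity, craving and negative affect.

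The session procedures (Procedures & Interventions, MBRP + tDCS Sessions) bear on how much dose a person can receive:

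- Breath alcohol: "Participants who have a BAC > 0.0 will be rescheduled".
- Withdrawal: "Subjects with CIWA scores of 8 or greater at any session will be excluded from the research study". Exclusion criterion 11 says the same.
- Maximum: "All participants will receive up to 8 two hour sessions of MBRP + tDCS, regardless of the group schedule".
- Schedule: "we will run groups either twice per week for four weeks or once per week for eight weeks". The stated reasons are availability of groups and therapists' schedules, not randomisation.

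On the analysis (Data Analysis/Statistical Considerations): "Variables associated with missing data and those used in randomization (gender, age, treatment history) will be covaried in all analyses". The mediation paragraph writes its model with treatment condition as the exposure. It gives no model for dose and no definition of attendance or practice.

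**The concern.** Attendance and practice arise after randomisation and are chosen by, or happen to, the participant. Attendance has an extra link to the outcome that the protocol itself creates. A person who has been drinking may be barred from a session, and one in withdrawal leaves the study. The same drinking plausibly predicts craving, mindfulness and drinking two months later. Fewer sessions can therefore go with more drinking even if the sessions do nothing, and the error favours the hypothesis.

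None of the covariates named for all analyses is a measure of drinking, so nothing planned is certain to break this link. The Background already associates engagement with MBRP with fewer and less severe lapses, so a dose association would readily be read as causal.

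Practice raises a separate issue. A total over treatment accumulates over 4 weeks in one schedule and 8 in the other, so it partly records which group a person joined.

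**Working it through.** **Number analysed.** The plan recruits 86, which follows from 74 for mediation: 74 × 1.15 = 85.1, rounded up to 86. With 15% attrition, 86 × 0.85 = 73.1, so n = 73 is used below.

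**Inputs the documents do not give.** They contain no rate of positive breath tests, no make-up rate and no correlation between drinking during treatment and at 2 months. On attendance they offer only experience from earlier trials: "MBRP treatment compliance rates range from 50-60% of participants attending the majority of sessions". The rest is assumed and varied.

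**Model, true dose effect zero.**

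- Drinking during treatment: u, standard normal.
- Outcome at 2 months: y = r·u + √(1 − r²)·noise.
- Mediator: correlated 0.4 with u.
- Chance of being barred at a session: logit⁻¹(logit(p) + ln(OR)·u).
- Sessions attended = sessions presented for − barred + made up.
- Tests: slope of y on sessions attended, two-sided 5%; mediated effect by joint significance of both paths.

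Mid case: p = 0.10, OR = 2 per SD, r = 0.5. At u = +1 the odds of being barred are 0.111 × 2 = 0.222, a probability of 0.18; at u = −1 they are 0.056, a probability of 0.05. Someone who presents for 75% of 8 = 6 sessions loses 6 × 0.18 = 1.1 sessions in the first case and 6 × 0.05 = 0.3 in the second.

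**False-positive rate for the total dose association, mid case:**

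| Rescheduled sessions made up and counted | No-show rate varies between people (median 25%) | Same 25% no-show rate for all |
|---|---|---|
| None | 14-15% | about 24-25% |
| Half | 7.5% | 10% |
| All | 5.3% | 4-5% |

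The right column is higher because less of the variation in attendance is unrelated noise. In the left column with none made up, the correlation is −0.11 and the spurious slope −0.47 SD per 8 sessions. With barring unrelated to drinking (OR = 1), the correlation is 0.00 and the rate 4.7%.

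**Other inputs, none made up, left-column model.** With r = 0.3 the rate is 8%; with r = 0.7 it is 25%. Across p from 2% to 20% and OR from 1.5 to 3 it runs from 5% to 57%. A harsher set (n = 86, r = 0.6, OR about 2.7 to 4.5 per SD, 20% of sessions missed at random) gives 23% to 94%.

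**Mediated effect.** The false-positive rate is 1.6% in the control, about 2-5% in mid cases and up to about 20% under the harsher set.

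**CIWA rule alone** (0.5-2% of sessions, OR 3): 6-18% if those excluded are followed and analysed, 5-6% if they have no analysed outcome.

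**Baseline adjustment.** Assume baseline drinks per drinking day correlates 0.5 with drinking during treatment and 0.4 with the outcome. In the mid case with none made up, the slope falls from −0.47 to −0.27 SD, a reduction of (0.47 − 0.27)/0.47 = 43%, and the false-positive rate from about 15% to 9%.

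**Attended divided by admissible sessions, as an alternative dose measure.** This does not solve the problem. When barring can occur only among those who come, false positives reach up to 35% even with random no-shows. If no-shows themselves depend on drinking (n = 86, p = 0.06, OR about 2.7), the rate is 22%, 58% and 92% for a no-show odds ratio of 1.2, 1.5 and 2.0 per SD. The ratio also stops measuring dose: 2 of 2 scores the same as 8 of 8.

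**Practice.** Treatment weeks available: 8 against 4, a ratio of 2. This biases the result only if a total is used and schedule is also related to outcome.

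**The case against.** The strongest reply is that the protocol says rescheduled, not refused. If every barred session is made up and counted, the breath-alcohol path vanishes, as the bottom row of the table shows. That stands as far as it goes. But the identical sentence is used for individual assessment visits, treatment runs in groups of 8-12 at set times, and the documents neither describe nor exclude make-up sessions. The point is open, and the plan should close it.

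A reader might infer that a dose effect will appear even when dose does nothing, or that the trial would report sessions working through mindfulness. The documents do not support that. They give none of the rates needed, most null trials in the mid cases show no significant association, and the mediated effect that Hypothesis 2 actually tests is falsely significant less often than the total association.

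Three further replies have force. The plan specifies no dose model, so the fault is a causal hypothesis without an analysis, not a biased model already written down. Baseline drinking could enter as a variable associated with missing data, but only if it happens to predict missingness. Home practice is not governed by the breath-alcohol or CIWA rules, and it is collected weekly for the prior week, so it can readily be expressed per week.

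**Conclusion.** The concern holds as a risk of bias in one clause of a secondary hypothesis. Attendance and practice are not randomised, attendance is tied by rule to current drinking, and no named covariate measures drinking. The bias runs towards more sessions going with less drinking.

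Under the assumed inputs, the total association is falsely significant in about 5% of trials if all rescheduled sessions are made up and counted, about 10% if half are, and about 15-25% in mid cases with none made up. Higher rates need extreme assumptions. The mediated effect stays at about 2-5% in mid cases and reaches about 20% only in extreme ones. The CIWA path adds little if excluded participants have no analysed 2-month outcome, and the documents do not say whether they are followed.

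The randomised comparison of active with sham tDCS is not affected.

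**What to change.** For the dose part of Hypothesis 2:

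1. Adjust for baseline drinks per drinking day, which is already collected. Where the Form 90 calendar allows, also adjust for drinking before each session. Earlier sessions may influence that drinking, so a marginal structural model is preferable to a plain covariate. The weekly battery as described has no drinking measure, so the calendar is the source.
2. Express practice per treatment week, with group schedule (4 or 8 weeks) as a covariate.
3. Log each session missed under the breath-alcohol or CIWA rule and whether it was made up, and state whether a made-up session counts as attended. Report a sensitivity analysis that counts the sessions the participant presented for (attended plus barred). It removes the breath-alcohol artefact only if no-shows are unrelated to drinking.
4. Do not use attended divided by admissible sessions as the main dose measure.
5. Report the result as a non-randomised association, not an effect of dose.

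These steps reduce the bias without removing it. The safety rules are unchanged. The cost is a reason code on the session record, where breath alcohol and CIWA are already taken, some analysis text, and a weaker claim for this secondary objective. Reasons for missed sessions are hard to recover later, so the log should be in place from the first group.
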